4.6 Subgroup Analyses

An additional subgroup DEXA analysis will be conducted for the first 8 subjects enrolled prior to [REDACTED] who received DEXA testing at Day 0 and Day 15, using the mean of these two values as baseline (with Day 15 data alone serving as the baseline for the analysis of the entire study population).

In addition, pre-specified subgroup analysis may be performed based on the following:

- Age (16-40; 41-64; >65 years; in addition, if patients between 12-16 are included in the trial, an additional age group analysis will be include for these patients to support inclusion of younger and pediatric patients into future studies.

- Gender
- BMI (greater vs less than the median BMI)
- Overall hyperphagia score (greater vs less than the median hyperphagia score)
- By growth hormone usage (yes or no)
- By institutionalized care situation (if permitted in the study; yes or no)

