4.2. Inclusion Criteria

Patients must meet all of the following inclusion criteria to be eligible for the study:

1. PWS due to chromosome 15 micro-deletion, maternal uniparental disomy, or imprinting defect, confirmed by fluorescent in situ hybridization, chromosomal microarray, and/or methylation studies. Obese male or female volunteers weighing at least 50 kg with BMI $\geq 27 \text{ kg/m}^2$.
2. Age 16-65 years
3. If a volunteer has diagnosis of type 2 diabetes, following criteria must be met:
 - a. HbA1c $<7.5\%$ not being managed with insulin. Patients taking GLP-1 analogues (exenatide or liraglutide) must have been on stable dose for at least 3 months.
 - b. Fasting plasma glucose $<140 \text{ mg/dL}$
 - c. No history of ketoacidosis or hyperosmolar coma
4. Vital signs must be within the following ranges and stable.
 - a. Systolic blood pressure, 90-150 mm Hg
 - b. Diastolic blood pressure, 50-90 mm Hg
 - c. Pulse rate, 40-100 bpm
5. Stable body weight at home for ~ 2 months (self or guardian-reported loss/gain within $\pm 5\%$).
6. Blood pressure ($\leq 150/90 \text{ mmHg}$); may include stable dose (≥ 30 days of use) of up to two anti-hypertensive medications that are intended to remain on a stable dose during the protocol
7. Parent or guardian is able to communicate well with the investigator, to understand and comply with the requirements of the study, and be able to understand and sign the written informed consent. Due to the significant intellectual disability with PWS, assent is to be provided by the patient who cannot consent for himself or herself.
8. Results of screening clinical laboratory tests (CBC with differential and platelets and chemistry profile) must be within normal range or, if outside of the normal range, must be accepted by the investigator and sponsor as not clinically significant.

9. Females of non-childbearing potential, defined as surgically sterile (status post hysterectomy, bilateral oophorectomy, or bilateral tubal ligation) or post-menopausal for at least 12 months (and confirmed with a screening FSH level in the post-menopausal lab range), do not require contraception during the study. All other females of child-bearing potential must agree to use contraception as outlined in the protocol.

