4.2.1 Derived Data

The following implementations will be made for derived data:

Table 1. Derived Variables

Variable	Derivation
General	
weight (kg)	weight (lb) \times 0.454; regardless of unit, take average of weight values for any one timepoint; if only 1 value is present for a timepoint, this value will be used in the analysis
height (cm)	height (in) \times 2.54
body mass index (kg/m ²)	weight (kg) / [height (m)] ²
temperature (°C)	[temperature (°F) - 32] \times 5/9
age (yr)	integer part of (date of informed consent - date of birth) / 365.25
Study Days and Periods	
relative day, prior to treatment with study drug	date of visit - date of study drug administration [Day 1 is the day immediately prior to treatment with first study drug in the placebo controlled run-in period.]
relative day, on or after day of study drug	date of visit - date of study drug administration + 1 [Day 1 is the day treatment with DB study drug was administered.]
relative time for efficacy endpoints	date and time of the evaluation - date and time of the end of the last injection of study drug
relative time for safety evaluations	date and time of the evaluation - date and time of the start of the first injection of study drug
Baseline	See Section 4.2.5
change from baseline	See Section 4.2.5

Abbreviations: C=Centigrade, F=Fahrenheit

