4.5 Efficacy Endpoints and Analyses

4.5.1 Primary Efficacy Endpoints

There will be 2 co-primary endpoints analysed.

Percent change from baseline in body weight, and percent change from baseline in the Overall score for the PWS Hyperphagia questionnaire over the 4-week double-blind dosing period (Period 2) will be assessed as co-primary efficacy endpoints.

The **Hyperphagia Questionnaire** is a 10-item instrument designed to measure food-related preoccupations and problems in PWS, as well as the severity of these concerns. Three factors identified from this questionnaire are:

- Hyperphagic Drive (e.g. how persistent in asking for food; how easy to direct away from food; items 1,3,6,9)
- Hyperphagic Behaviors (e.g. how fast or clever in obtaining food; how often steal food; items 2,4,5,8)
- Hyperphagic Severity (time spent talking about food; extent that food interferes with everyday functioning; items 7,10)

Items are rated by care providers on a 5-point scale (1=not a problem to 5=a severe and/or frequent problem). The questionnaire can be found in Appendix 2. Raw scores for each factor will be used in data analyses, and the three domains will be summed for an overall summary index of hyperphagia (maximum overall score of 50). Missing values will not be imputed. If a single item in a factor is missing for a patient, that factor will be missing.

These endpoints will be tabulated by dose group for the FAS and PP populations. There will be no adjustment for multiplicity.

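### SAP 4.6: the optional age cuts include a group no eligible patient can enter and leave age 65 unassigned, and the median splits have no rule for patients at the median

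*SAP*

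**What the plan says.** The subgroup list in SAP 4.6 is introduced as "pre-specified subgroup analysis may be performed based on the following", so the analyses are named in advance but need not be done. Three of its entries matter here:

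- Age: "Age (16-40; 41-64; >65 years; in addition, if patients between 12-16 are included in the trial", in which case a further age group is analysed for those patients.
- BMI: "BMI (greater vs less than the median BMI".
- Hyperphagia: "Overall hyperphagia score (greater vs less than the median hyperphagia score".

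Protocol 4.2, criterion 2, sets eligibility at "Age 16-65 years", and the synopsis gives the same range. SAP 4.2.1 derives age as "integer part of (date of informed consent - date of birth) / 365.25", that is, completed years at consent. SAP 4.5.1 describes the questionnaire as having ten items: "Items are rated by care providers on a 5-point scale (1=not a problem to 5=a severe and/or frequent problem". It adds that "the three domains will be summed for an overall summary index of hyperphagia (maximum overall score of 50". Neither document gives other cuts or says where a value equal to the median goes.

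**The concern.** A set of subgroups should place each patient in exactly one group. Read against the eligibility criterion and the SAP's own age derivation, the age list does not: one group is empty by design and one eligible age has no group. The two median splits use strict inequalities on both sides, so a patient at the median satisfies neither. This matters most for the hyperphagia score, which takes few distinct values.

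The stakes are modest. SAP 1 says the study is meant to explore populations and age-related effects as a basis for Phase 3, and the subgroups come from only about 36 patients. If the tie rule is left open, someone has to choose which half receives the tied patients, possibly after seeing results. Naming the subgroups in advance is meant to prevent that choice.

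**Working it through.** SAP 4.6 states no figure of its own, so there is nothing to reproduce first.

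**Age.** Inputs: eligible ages 16 to 65 (Protocol 4.2), whole-year age (SAP 4.2.1) and the cuts in SAP 4.6. Assign each of the 65 − 16 + 1 = 50 eligible whole-year ages:

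| Derived age | 16-40 | 41-64 | >65 | 12-16, if used |
|---|---|---|---|---|
| 16 | yes | no | no | yes |
| 17 to 40 | yes | no | no | no |
| 41 to 64 | no | yes | no | no |
| 65 | no | no | no | no |

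No eligible age exceeds 65, so the third group has 0 patients. Age 65 is in no group. Age 16 is in two groups only if the extra younger group is used. Because age is truncated to whole years, there is no gap between 40 and 41.

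**Hyperphagia score: range.** Ten items scored 1 to 5 give a minimum of 10 × 1 = 10 and a maximum of 10 × 5 = 50. The maximum agrees with SAP 4.5.1, and the overall score is an integer.

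**When someone is at the median.**

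- Odd N: the median is one patient's own value, so at least one patient is always at it.
- Even N: the median is the midpoint of the two middle values, so a patient is at it only if those two values are equal.

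**How often, at N = 36.** The documents give no mean or SD for this score. Assumption: rounded normal scores, mean 28, limited to 10-50, SD 5 to 10, with 20,000 simulated trials per setting. The average loss over all trials is P(anyone at the median) × mean number at the median when anyone is.

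| Assumed SD | P(anyone at median) | Mean number when anyone is | Mean over all trials | Share of 36 |
|---|---|---|---|---|
| 5 | 0.67 | 4.2 | 0.67 × 4.2 = 2.8 | 7.8% |
| 6 | 0.62 | 3.8 | 0.62 × 3.8 = 2.4 | 6.5% |
| 8 | 0.53 | 3.3 | 0.53 × 3.3 = 1.7 | 4.9% |
| 10 | 0.46 | 3.0 | 0.46 × 3.0 = 1.4 | 3.8% |

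Repeating this with mean 30 gives probabilities of 0.67, 0.54 and 0.47 for SD 5, 8 and 10, and average losses of 2.8, 1.8 and 1.4. The choice of mean hardly matters.

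**At N = 35.** With mean 30, the probability is 1 and the average number at the median is 3.7, 2.7 and 2.4 for SD 5, 8 and 10. An odd N is quite possible. Enrolment is only approximately 36, the FAS needs a baseline and a post-baseline value (SAP 3.4), and one missing item makes a domain score missing (SAP 4.5.1).

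**BMI.** Assuming mean 40, SD 8 and one decimal place, someone is at the median in about 8% of trials at N = 36, with 0.2 patients lost on average. At N = 35 someone always is, 1.2 patients on average.

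**The case against.** The strongest reply is that nothing important hangs on this. The subgroup analyses are optional, SAP 4.2.4 makes no multiplicity adjustment, and the primary and key secondary analyses use the whole FAS and PP sets. SAP 1 leaves confirmation to Phase 3. All of that stands, and it makes this a minor point.

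Other parts of the reply limit the claim:

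- A reader might infer that the SAP orders tied patients to be discarded. It does not; it is silent on ties, and a programmer may well supply a rule. The defect is a missing rule, and the loss arises only under a literal reading.
- A reader might quote the loss as 3.0 to 4.2 patients (8% to 12%). Those figures apply only to trials in which a tie occurs. In 33% to 54% of the simulated trials of 36 patients nobody is at the median.
- A reader might treat BMI like the hyperphagia score. BMI is nearly continuous, because weight is averaged over repeat readings (SAP 4.2.1), so ties are uncommon at even N.
- A reader might count the overlap at age 16 as a present error. Protocol 4.2 admits nobody under 16, and the 12-16 group is an additional analysis used only if such patients enter.

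Finally, the third age cut may be a slip for 65 and over. The text available cannot settle that. If so, age 65 would be assigned, but the group would span one eligible year of age. As printed, the gap and the empty group stand.

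**Conclusion.** The point holds, at low importance. Two age defects follow from the text without any assumption beyond reading age in whole years: the group above 65 is empty for eligible patients, and age 65 is unassigned. How many patients are aged 65 is unknown and may be none, since the documents give no age distribution.

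The missing tie rule is also a matter of text, but its size rests on assumed score distributions. For the hyperphagia score at N = 36 and SD 5 to 10, a literal reading loses someone in about 46% to 67% of trials, and on average about 1.4 to 2.8 patients (4% to 8%) over all trials. With an odd N a loss is certain. For BMI the practical effect at even N is small.

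It would go too far to infer from this that efficacy results are biased or that patients leave the main analysis. The documents confine the effect to exploratory subgroup tables.

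**What to change.** Amend SAP 4.6 before unblinding:

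- Age groups 16-40 and 41-65. If younger patients are admitted, define the extra group as under 16.
- BMI and overall hyperphagia score: at or below the median versus above the median.
- For both splits, take the Day 15 baseline value (the Period 2 baseline in SAP 4.2.5) and compute the median over the FAS.

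Every eligible patient with the baseline value then falls in exactly one group. The halves may be unequal when there are ties, but nobody is left out. The cost is a line or two of SAP wording, with no effect on trial conduct, data collection or the primary analysis.

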Study Population	Obese males and females with confirmed diagnosis of PWS, due to chromosome 15 micro-deletion, maternal uniparental disomy, or imprinting defect, and a Body Mass Index (BMI) greater than or equal to 27 kg/m ² who are able to have study medication administered by a health care professional or trained caretaker. Subjects with type 2 diabetes (HbA1c <7.5.0%) will be allowed to enter the study.
Number of Patients & Study Centers	Number of patients to be targeted: approximately 36 Study Center: Up to 8
Inclusion Criteria	
 1. PWS due to chromosome 15 micro-deletion, maternal uniparental disomy, or imprinting defect, confirmed by fluorescent in situ hybridization, chromosomal microarray, and/or methylation studies. Obese male or female volunteers weighing at least 50 kg with BMI ≥ 27 kg/m². 2. Age 16-65 years. 3. If a volunteer has diagnosis of type 2 diabetes, following criteria must be met: 
 a. HbA1c <7.5% not being managed with insulin. Patients taking GLP-1 analogues (exenatide or liraglutide) must have been on stable dose for greater than 3 months. b. Fasting plasma glucose <140 mg/dL

- c. No history of ketoacidosis or hyperosmolar coma
- 4. Vital signs must be within the following ranges and stable:
 - a. Systolic blood pressure, 90-150 mm Hg
 - b. Diastolic blood pressure, 50-90 mm Hg
 - c. Pulse rate, 40-100 bpm
- 5. Stable body weight at home for ~2 months (self or guardian-reported loss/gain within \pm 5%).
- 6. Blood pressure (\leq 150/90 mmHg); may include stable dose (\geq 30 days of use) of up to two anti-hypertensive medications that are intended to remain on a stable dose during the protocol.
- 7. Parent or guardian is able to communicate well with the investigator, to understand and comply with the requirements of the study, and be able to understand and sign the written informed consent. Due to the significant intellectual disability with PWS, assent is to be provided by the patient who cannot consent for himself or herself.
- 8. Results of screening clinical laboratory tests (CBC with differential and platelets and chemistry profile) must be within normal range or, if outside of the normal range, must be accepted by the investigator and sponsor as not clinically significant.

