1 INTRODUCTION

This document presents the statistical analysis plan (SAP) for Rhythm Pharmaceuticals, Inc. (Rhythm), Protocol No. RM-493-010: A Phase 2, Randomized, Double-Blind, Placebo-controlled Pilot Study to Assess the Effects of RM-493, a Melanocortin 4 Receptor (MC4R) Agonist, in Obese Subjects with Prader-Willi Syndrome (PWS) on Safety, Weight Reduction, and Food-Related Behaviors.

It contains the details and methods to be used to perform the proposed efficacy and safety analyses, including planned summary tables and by-patient listings.

This SAP was based on [REDACTED]. The reader of this SAP is encouraged to also read the clinical protocol, and other relevant documents for details on the planned conduct of this study. Other than the schedule of study procedures which is provided in Appendix 1, operational aspects related to collection and timing of planned clinical assessments are not repeated in this SAP unless relevant to the planned analyses.

The objectives listed below (primary, secondary and exploratory) are found in the protocol.

Study RM-493-010 is a Phase 2 study designed to provide the basis for pivotal data in a Phase 3 study or studies to follow. The PWS population is very rare, and patients are difficult to identify and recruit. Therefore the number of participants studied will be small. In addition, there is no precedent for an approved effective treatment for the hyperphagia and obesity of PWS. As a consequence, endpoints have not been well studied, and key questions on tools, endpoints, populations, age-related effects, and other parameters remain to be answered. This study has been designed to explore these questions, and to provide a rationale for a more robust Phase 3 study design. As a result of the small number of patients and the lack of clarity on clinically important endpoints for PWS, this study includes numerous endpoints for which no multiplicity adjustment is planned. It will also include an interim analysis when approximately half the patients have been randomized, with the likelihood that study parameters may be altered and adjusted to reflect additional understanding of the effects of setmelanotide in this population. This approach is justified given the evolving understanding of PWS and any information and/or conclusions will be confirmed in a prospective, rigorous Phase 3 study or studies to follow.

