4.4.3 Demographic and Disease Characteristics

Demographic data will include patient age, gender, race, and ethnicity. Baseline characteristics include weight, height, BMI, and waist circumference. Demographic and baseline characteristics will be tabulated for all patients in the SAF population by dose group and overall.

A by-patient listing will be presented for all patients in the SAF population.

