4.5.1.1 Primary Analysis

The primary analysis involves comparison of percent change from baseline during Period 2 between the RM-493 active treatment groups and placebo. A mixed model repeated measures analysis of variance with fixed terms for treatment, time, treatment-by-time interaction and baseline covariate as well as a random effect for subjects will be used to assess the primary efficacy endpoint. An unstructured covariance matrix will be used to model the expected different variances among the treatments. T-tests derived from the model will use Satterthwaite's degrees of freedom estimates.

The assumption of normality will be assessed via the Shapiro-Wilk statistic as a diagnostic of closeness to normality, not as a conditional test associated with efficacy endpoint analyses. Other graphical assessments of residuals from the model fit may be examined. If a substantial departure from normality is observed, a transformation such as log (post/pre) or rank may be used to analyze the data as a sensitivity analysis; however, the analysis on the original scale of observation will be reported.

The comparison of each dose of RM-493 with placebo will be carried out via 1-sided statistical test at alpha=0.05, with no adjustment for multiplicity for comparisons with two dose regimens. Of note, the 0.5 mg dose was included in the study as an anticipated no-effect or minimal effect dose for dose ranging.

Least square (LS) mean changes from baseline for each treatment group, and LS mean difference between each active RM-493 dose group and placebo, and the associated 95% confidence intervals for the difference will be provided, along with the reported p-values (one-sided). In addition change from baseline will be tested using a 2-sided statistical test at alpha=0.05.

Sample SAS code that can be used to implement the MMRM analysis is provided below:

```
proc mixed data=adef method=reml;
  class subjid trtpn visitnum;
  model pcgresn = trtpn visitnum trtpn*visitnum base / solution ddfm=satterthwaite;
  repeated visitnum / type=un subject=subjid;
  lsmeans trtpn*avisitn / cl alpha=0.05;
  lsmeans trtpn*avisitn / diff=control ('1' 'Day x') cl; *[where '1' represents group=placebo];
run;
```

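### If the optional subgroup analyses in SAP 4.6 are run, median splits of BMI and hyperphagia score should be accompanied by a treatment-by-continuous-baseline interaction estimate

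*SAP*

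**What the plan says.** SAP 4.6 (Subgroup Analyses) introduces its list with "In addition, pre-specified subgroup analysis may be performed based on the following". Two of the factors are continuous measures cut at the median: "BMI (greater vs less than the median BMI" and "Overall hyperphagia score (greater vs less than the median hyperphagia score". Age is cut into bands. The section gives no model, test or interaction term for any factor.

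The gap is not filled elsewhere. The primary model in SAP 4.5.1.1 has "fixed terms for treatment, time, treatment-by-time interaction and baseline covariate", so baseline enters as a main effect only and the sole interaction is with time. SAP 4.7 covers correlations of pharmacokinetics, efficacy endpoints and instruments, not baseline modifiers of the drug effect.

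Both measures are held as numbers. SAP 4.4.3 states "Baseline characteristics include weight, height, BMI, and waist circumference". In SAP 4.5.1, "the three domains will be summed for an overall summary index of hyperphagia (maximum overall score of 50". With ten items rated 1 to 5, that score runs from 10 to 50.

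The purpose is set out in SAP 1: "key questions on tools, endpoints, populations, age-related effects, and other parameters remain to be answered". The study is meant to explore these questions and to inform a Phase 3 design.

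**The concern.** Whether the drug effect depends on BMI, age or severity of hyperphagia is one of the questions this pilot is meant to explore. With about 36 patients, the way that question is put to the data matters. A median split treats a patient just above the median like the most extreme patient and so discards information already collected.

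Without an interaction estimate, the natural reading of a split is to compare the two halves by eye or by their separate p-values. A significant result in one half and not in the other is not evidence that the effects differ. A Phase 3 population could then be narrowed, or a baseline factor emphasised, on the strength of noise.

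**Working it through.** **1. The plan's own figure.** SAP 4.1 gives SDs of 1.1 kg (placebo) and 2.3 kg (RM-493), 12 v 12, one-sided 5%.
- SE = √(1.1²/12 + 2.3²/12) = 0.736 kg, with 15.8 Satterthwaite df.
- Unequal-variance t-test power is 94.5% at 2.5 kg (stated 94%) and 83.0% at 2 kg (stated 83%).
- Minimum significant difference is 1.747 × 0.736 = 1.29 kg (stated 1.3).

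The stated figures reproduce. The documents give no figure for the subgroup analyses.

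**2. Numbers per group.** Applying 2:1:3 to about 20 and then about 16 patients:
- placebo: 20×2/6 + 16×2/6 = 12
- 0.5 mg: 20×1/6 = 3.3
- 1.5 mg: 20×3/6 + 16×1/6 = 12.7
- 2.5 mg: 16×3/6 = 8

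A half therefore holds about 6 placebo, 1 to 2 at 0.5 mg, 6 at 1.5 mg and 4 at 2.5 mg.

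**3. Information lost by the split.** For a linear effect, the share kept is the squared correlation between the variable and its above-median indicator. For a normal variable this is (0.399/0.5)² = 2/π = 0.637, a loss of 36.3%. Then 36 patients carry the information of 36 × 0.637 ≈ 23.

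| Assumed shape | Loss |
|---|---|
| Uniform | 25% |
| Normal, mean 38, SD 8, cut off at BMI 27 | 34% |
| Score rounded to 10–50, mean 30, SD 8 | 36% |
| Gamma, skew 1 | 41% |
| Lognormal, skew 1.3 | 44% |
| Exponential | 52% |

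The cut-off in the second row is the entry criterion, "Body Mass Index (BMI) greater than or equal to 27 kg/m"². The means, SDs and shapes are assumptions.

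**4. Testing each half separately when the true effect is the same in both.** With power p in each half, exactly one half is significant with probability 2p(1 − p). SAP SDs, one-sided 5%, unequal-variance t-test:

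| Active v placebo per half | True effect | SE | p | 2p(1 − p) |
|---|---|---|---|---|
| 6 v 6 | 2.5 kg | 1.041 | 0.699 | 42% |
| 6 v 6 | 2.0 kg | 1.041 | 0.537 | 50% |
| 4 v 6 | 2.5 kg | 1.235 | 0.510 | 50% |
| 4 v 6 | 2.0 kg | 1.235 | 0.381 | 47% |

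Separate simulations gave 42% to 51%.

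**5. Power for the interaction.** Simulated linear model with treatment, factor and their product; normal factor; two-sided 5%. The slopes are assumptions.

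| Setting | Continuous | Split |
|---|---|---|
| 24 v 12, SAP SDs, 1 kg per SD, common-variance test | 20% | 12% |
| Same, variance estimated by arm | about 36% | about 25% |
| 13 v 12, SAP SDs, 1 kg per SD, variance by arm | 24% | 17% |
| 8 v 12, SAP SDs, 1 kg per SD, variance by arm | 16% | 12% |
| 24 v 12, equal SDs, 0.5 residual SD per SD | 25% | 16% |
| 24 v 12, equal SDs, 1 residual SD per SD | 70–72% | 45–47% |

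The rows with variance by arm come from a check of 6,000 to 8,000 trials per setting: separate residual variances, Satterthwaite df. In that check the common-variance test had a false-positive rate of about 2% at 24 v 12 and 9% at 8 v 12. With variance by arm it was about 5% throughout. Unequal variances therefore have to be allowed for.

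**6. If the effect is a step, not a line.** With the effect stepping by ±0.8 residual SD at the population median (24 v 12, equal SDs), the ranking reverses: continuous about 35%, split about 44%.

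**The case against.** The analyses only may be performed, there is no multiplicity control (SAP 4.2.4), and SAP 1 says conclusions will be confirmed in Phase 3. No trial conclusion depends on the splits. All of this stands and keeps the point minor.

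A reader might infer that the SAP plans significance tests within halves and so invites false subgroup claims. The text does not support that: SAP 4.6 specifies no test, and descriptive summaries would comply. The 40% to 50% figure is a warning about one way the splits could be read, not a description of the plan.

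A reader might also infer that a continuous interaction would show who responds. That rests on large modifiers. One residual SD per baseline SD is about 1.8 kg (root mean square of 1.1 and 2.3), which would move a 2.5 kg effect from about 0.7 to 4.3 kg between −1 and +1 SD. Nothing in the documents supports so strong a modifier. The 24 v 12 setting also pools all doses, which SAP 4.2 allows only if the active groups show similar efficacy, while Protocol 3.4 reports minimal efficacy at 0.5 mg.

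The linearity objection stands in part. A step favours the split, and with skewed BMI a few extreme patients could drive the slope. Hence the splits should stay as a display.

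**Conclusion.** The point holds as a low-cost improvement to an optional, exploratory analysis. The plan cuts BMI and the Overall hyperphagia score at the median and names no treatment-by-baseline interaction, although the continuous values are available.

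Under a roughly linear effect and a roughly normal baseline, the split loses about 36% of the information on effect modification, and an interval from it would be about 1/√0.637 = 1.25 times as wide. Power remains low at plausible sample sizes and modest slopes with either method. The benefit is a more precise estimate with an honest interval, and protection against reading a difference in p-values as a difference in effect. No primary result is affected.

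**What to change.** In SAP 4.6, state that if subgroup analyses are run, each continuous factor (BMI, Overall hyperphagia score, age) is also analysed by a treatment-by-continuous-factor interaction, one factor at a time:

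- **Target.** The Day 42 effect. A Day 42 model is simplest; within the repeated-measures model, treatment-by-factor-by-visit terms would be needed.
- **Terms.** Keep the main effect of the factor and allow residual variance to differ by arm. The sample code in SAP 4.5.1.1 fits one covariance matrix for all arms, so it would need changing.
- **Output.** The slope difference with its 95% interval, and the drug effect at the 25th and 75th percentiles of the factor.
- **Comparisons.** 1.5 mg v placebo and 2.5 mg v placebo; pooled active only under the SAP 4.2 condition. No separate slope for 0.5 mg, which rests on about 3 patients.
- **Hyperphagia score as modifier of the hyperphagia endpoint.** Use change, or the Day 42 score, adjusted for baseline. Percent change has the modifier as its denominator.
- **Median splits.** Keep them as descriptive displays, which also show gross non-linearity. Use no within-half p-values as evidence of a different effect. State which half takes scores equal to the median, since the score is an integer.

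The cost is SAP text and a short extra model per factor and comparison; no new data. The downside is the linearity assumption: a step-shaped effect would be detected somewhat better by the split.
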